7.2.2 Clinical Experience

Due to routine childhood vaccination with tetanus toxoid, universal class II binding peptides from tetanus toxoid (P30 and P2 epitopes) have a well-established safety record and pre-existing immunity to the P2 and P30 epitopes is highly likely in all patients. The tetanus toxoid-derived P2 and P30 class II helper epitopes have long history of being used as CD4⁺ helper epitopes and have been combined with other antigens as separate peptides [51] and as a fusion peptides in clinical trials [26, 52].

pp65

Our group has 10 years of experience in vaccinating subjects with CMV pp65-LAMP loaded DCs. While the type of vaccination is different, our experience with CMV pp65-LAMP loaded DC vaccines is pertinent to this protocol. In the ATTAC trial (NCT00639639), patients were randomized to receive CMV pp65-LAMP DC vaccination following tetanus toxoid or unpulsed DC pre-conditioning at the vaccine site. In the ATTAC GM trial, patients were vaccinated with CMV pp65-LAMP DCs mixed with GM-CSF (Granulocyte macrophage colony-stimulating factor) [53]. In the ERADICATE study (NCT00693095), patients received CMV pp65-LAMP DCs and CMV-specific adoptive lymphocyte transfer [54]. In the REGULATE study (NCT00626483), patients received CMV pp65-LAMP DCs in combination with anti-CD25 monoclonal antibody (mAb) treatment (Basiliximab) to remove regulatory T cells (T_{Regs}). In the completed ELEVATE study under IND 16,301 (NCT02366728), subjects were treated with CMV pp65-LAMP DCs in combination with TMZ and either tetanus diptheria toxoid (Td) or unpulsed DC pre-conditioning. In the completed AVERT study under IND 16,301 (NCT02529072), patients received CMV pp65-LAMP DCs in combination with the anti-PD-1 mAb Nivolumab. The ongoing phase 2 “ATTAC II” trial (NCT02465268), a multi-site trial at the University of Florida and Duke, is investigating whether the addition of pp65-LAMP DC vaccines plus GM-CSF and Td to dose-intensified TMZ treatment is worthy of investigation in a larger phase 3 trial. In aggregate, we have given CMV pp65-LAMP DC vaccines to over 115 patients in combination with a number of agents. The CMV pp65-LAMP DCs have been well tolerated with no serious or off-target toxicities to date.

These data suggest that the AE reactions following PEP-CMV vaccination are indeed immune-related. The cumulative data indicate that PEP-CMV vaccination is inducing the activation of T cells specific for the target antigen pp65. Furthermore, in patients with AEs, the pp65-specific T cell activation may be inducing a temporary elevation of pro-inflammatory cytokines. We believe that the vaccine reactions we have been observing in PERFORMANCE are likely indicative of vaccine potency. Patients who have demonstrable Grade 3 reactions also have measurable cellular responses to the PEP-CMV vaccines, which may be indicative of clinical responses, and can be easily managed through standard premedication with Tylenol, Benadryl, or Zofran as has been used in other trials with similar immune-related AEs. The reactions typically occurred 2-4 hours after vaccine administration, and most patients were generally discharged the same day or the following day with a few patients who were discharged 2-4 days post reaction. The most significant reactions in some patients included grade 3 hypotension, grade 1 tachycardia, grade 3 lactic acidosis, and grade 3 flu-like symptoms with fever (up to 39°C).

It is important to note that the T cell responses in PERFORMANCE may be solely mediated by pp65-specific CD4⁺ T cells activated by class II epitopes found in the long pp65 vaccine. These class II epitopes are not present in the pp65-P30 linked vaccine that contains only the class I pp65 HLA-A*0201 restricted NLVPMVATV epitope. Therefore, the pp65-P30 peptide has important differences from the long pp65 peptide used in PERFORMANCE.

A peptide very similar to what we are proposing was used in two phase 1b clinical trials and contained the NLVPMVATV epitope linked to a different universal class II binding sequence from the P2 epitope of tetanus toxoid (TT₈₃₀₋₈₄₃ QYIKANSKFIGITE) and included adaptor (KSS) and linker (AAA) sequences (KSSQYIKANSKFIGITEAAANLVPMVATV). When given with the adjuvant PF03512676 in both CMV seropositive and seronegative HLA-A*0201 positive healthy volunteers, this peptide had an acceptable safety profile and induced the expansion of CMV-specific T cells [57]. Volunteers received escalating doses of peptide with most AEs being Grade 1 or 2 including injection site reactions or systemic mild flu-like symptoms, which resolved within 1 to 2 days. One patient (7.7%) experienced a Grade 3 AE including malaise, fever and urticaria, which

resolved with non-prescription analgesics within 8 days. When given with the adjuvant PF03512676 in 18 CMV seropositive HLA-A*0201 positive patients undergoing hematopoietic stem cell transplantation, this peptide was safe, expanded CMV-specific T cells, and only one patient experienced an AE related to vaccination (Grade 1 fever) [58]. It is expected that the vaccine will be even safer in the HLA-A*0201 subjects who will be included in this trial.

EphA2

The EphA2_{883–891} (TLADFDPRV) epitope as a separate peptide has been used in several trials in patients with glioma [27, 31]. In one trial, over 70% of the HLA-A*0201 positive patients demonstrated EphA2-specific T cells after vaccination [27]. In this prior study, a synthetic peptide representing the same EphA2_{883–891} epitope was given with other peptides at a dose of 300 µg/peptide/dose via subcutaneous vaccinations in combination with 20 µg/kg intramuscular (i.m.) injections of poly-ICLC to HLA-A2⁺ adults with low grade glioma [27]. AEs included grade 1 and 2 injection site reactions (100%) and flu-like symptoms (fatigue, myalgias, fever, headache), which were usually limited to 48 hours after each vaccine and were controlled with acetaminophen or ibuprofen. Three patients developed grade 1 leukopenia and one patient developed a grade 3 fever after the seventh vaccine that resolved with a nonsteroidal anti-inflammatory drug the next day.

The same research group also gave the EphA2_{883–891} epitope as part of a similar TAA multi-peptide vaccine to HLA-A*0201 positive pediatric patients with newly diagnosed malignant brainstem and non-brainstem glioma [59]. Twenty-six patients were enrolled to receive the TAA vaccine that included the P2 epitope (TT_{830–845}) in Montanide ISA-51, in combination with 30 µg/kg i.m. injections of Hiltonol[®]. Vaccines were given three weeks apart for eight courses of vaccination followed with booster vaccination every six weeks. Toxicities were mild and included injection site reactions (100%), flu-like symptoms (92%), Grade 1 GI symptoms (31%), Grade 1 leukopenia (15.4%), and no Grade 3 or higher toxicities. Eleven children showed cellular immune responses to the EphA2 epitope after vaccination.

Survivin

The TAA survivin has been shown to be overexpressed in a variety of human cancers including malignant glioma [60]. In patients with breast cancer, melanoma and chronic lymphocytic leukemia, T cell responses to the class-I HLA-A*0201 restricted survivin epitope that we will use (Survivin_{95–104} ELTLGEFLKL) have been detected [61]. These data demonstrate that endogenous immunity to the survivin_{95–104} epitope spontaneously develop in patients with cancer. Furthermore, the survivin_{95–104} epitope has been shown to expand T cells from HLA-A*0201 healthy donors [61].

A highly similar artificial epitope (survivin_{96–104:M2} LMLGEFLKL) was given along with the EphA2_{883–891} epitope in the same study published by Okada *et al* described above. In this study survivin_{96–104:M2} LMLGEFLKL was given with other TAA peptides (including EphA2_{883–891}) at a dose of 300 µg/peptide/dose via subcutaneous

vaccinations in Montanide ISA-51, in combination with 20 µg/kg i.m. injections of Hiltonol® to HLA-A2⁺ adults with low grade glioma [27]. In comparison to survivin₉₅₋₁₀₄, survivin_{96-104:M2} is one amino acid shorter and was created to include a modified second amino acid (T to M) to further increase binding strength and T cell activation. In this multi-peptide vaccine, the tetanus derived P2₈₃₀₋₈₄₅ epitope was also included as a separate class II-binding helper peptide. Immune responses to survivin were detectable and AEs included grade 1 and 2 injection site reactions (100%) and flu-like symptoms (fatigue, myalgias, fever, headache), which were usually limited to 48 hours after each vaccine and were controlled with acetaminophen or ibuprofen. Three patients developed Grade 1 leukopenia and one patient developed a Grade 3 fever after the seventh vaccine that was resolved with a nonsteroidal anti-inflammatory drug the next day. This study indicates that a tetanus-derived helper peptide when given separately with a modified Survivin₉₅₋₁₀₄ (survivin_{96-104:M2}) I epitope was safe and could generate survivin-specific T cells. As outlined above for EphA2, the same research group also gave the modified survivin_{96-104:M2} peptide as part of a similar TAA multi-peptide vaccine to HLA-A*0201 positive pediatric patients with newly diagnosed malignant brainstem and non-brainstem glioma [59]. No Grade 3 or higher toxicities were observed and immune responses to survivin were detected in 3 of 21 children.

7.3 Study Purpose/Rationale

This safety study will also be a proof of concept trial design. Patient numbers can be increased if replacements are needed.

The primary objective for the trial described here is to evaluate the safety profile of a cancer vaccine comprised of P30-linked EphA2, CMV pp65, and survivin peptides, and secondarily to assess if P30-linked vaccination increases the number of P30-EPS-specific polyfunctional T cells.

8 OBJECTIVES AND ENDPOINTS

	Objective	Endpoint	Analysis
Primary	Evaluate the safety profile of a cancer vaccine comprised of P30-linked CMV pp65, EphA2 and survivin peptides	Percent of patients who experience DLT within each stratum at each dose level	See Section 15.5
Secondary	Assess whether pp65-specific polyfunctional T cells increase after priming vaccination with the P30-linked pp65 peptide.	Among CMV seropositive patients, mean fold increase in pp65-specific T cells between day 1 and day 22 in patients, and day 1 and 84. Among CMV seronegative patients, percent of patients who develop pp65-specific polyfunctional T cells between day 1 and 22, and day 1 and 84.	See Section 15.6.1
Secondary	Assess whether EphA2- or survivin-specific polyfunctional T cells increase after priming vaccination with P30-linked EphA2 or survivin peptides.	Among all patients, mean fold increase in EphA2- or survivin-specific T cells between day 1 and day 22, and day 1 and 84	See Section 15.6.2
Secondary	Assess whether pp65-specific polyfunctional T cells increase after booster vaccination with the P30-linked pp65 peptide.	Among CMV seropositive patients, mean fold increase in pp65-specific T cells between day 84 and day 140. Among CMV seronegative patients, percent of patients who develop pp65-specific polyfunctional T cells between day 84 and day 140.	See Section 15.6.3
Secondary	Assess whether EphA2- or survivin-specific polyfunctional T cells increase after booster vaccination with P30-linked EphA2 or survivin peptides.	Among all patients, mean fold increase in EphA2- or survivin-specific T cells between day 1 and day 84 and 140.	See Section 15.6.4

	Objective	Endpoint	Analysis
Other Secondary	Describe the survival and PFS of patients who received a vaccine comprised of P30-linked pp65, EphA2 and survivin peptides.	Median survival Median PFS	See Section 15.6.5
Exploratory	Assess the diversity of the P30-EPS-specific memory T cell repertoire via TCR sequencing.	Median change in normalized entropy between baseline (pre-vaccine #1) and after vaccine #5. Entropy is a measure of clonal expansion, or the extent of TCR repertoire expansion.	See Section 15.7.1
Exploratory	Define the relationship between reported biomarkers of response to immunotherapy in GBM and survival.	Association between the following: tumor mutational burden (TMB), tumor-intrinsic Erk1/2 signaling; TMEM119+ (microglia) cell density; peripheral Ki67+ CD8 T cells; and gene expression signatures of MHC-class II, IFN- γ , and cell cycle/proliferation.	See Section 15.7.2
Exploratory	Assess resected tumor for the expression of vaccine targets (i.e. EphA2, pp65, and survivin).	Association between the vaccine targets (EphA2, pp65, and survivin) and clinical outcomes	See Section 15.7.3
Exploratory	Assess changes in the tumor immune microenvironment, mutational heterogeneity/clonality, neoantigen depletion, and their association with survival.	Association between putative neoantigen depletion, mutational heterogeneity, gene expression signatures of T cell inflammation, and their relationship with survival.	See Section 15.7.4

9 INVESTIGATIONAL PLAN

9.1 Study Design

The proposed study is designed to assess the safety of administering a cocktail of three TAA peptides (P30-EPS) mixed with Hiltonol® in patients with newly diagnosed WHO grade 4 malignant glioma. In addition to assessing safety, blood draws will be performed at baseline and throughout the study to investigate how the immune system changes in response to P30-EPS peptide vaccination. We will also request archival tumor tissue from patients' baseline surgical resection or prior biopsy, as well as tumor

tissue from future surgeries, but only in the case that the patients may undergo other clinically indicated biopsy or tumor resection while participating in this study. Available tumor tissue will be analyzed by correlative analyses as outlined in Section 9.3.

A maximum of 36 patients will be accrued to the study after providing informed consent. Patients will consent to this study after completion of XRT/TMZ, as long as they will be able to start treatment within eight weeks of the end of XRT/TMZ (and as long as this is felt to be in the best interest of the patient by the treating physician). After providing informed consent, patients will undergo screening to confirm study eligibility. Both CMV seropositive and seronegative patients will be allowed on study. Because CMV seropositive patients have previously been infected with CMV, they will have pp65-specific memory T cells. CMV seronegative patients will only have naïve pp65-specific T cells. We will evaluate the impact of vaccination on both pp65-specific memory or pp65-specific naïve T cell expansion.

Regardless of when they enroll, all patients will undergo the same vaccination schedule. Dose escalation will be performed separately among CMV seropositive and seronegative patients. Within each of these strata, vaccines will initially contain 300 µg of each peptide (P30-linked EphA2, pp65, and survivin peptides) pooled in 10% dimethyl sulfoxide (DMSO) in water and mixed with 20 µg/kg of Hiltonol®. Within each stratum, the first 3 patients will be treated with 300 µg/peptide/dose. The enrollment of the first 2 patients treated with 300 µg/peptide/dose within each CMV stratum will be staggered by 2 weeks. Dose escalation to 400 µg of each peptide is planned; however, there are contingencies to reduce the dose to 200 µg of each peptide if 300 µg is not safe. If further dose reduction is needed, the pp65 peptide will be removed from the vaccine combination (See Section 15.5.1.2). Patients will undergo standard of care XRT with or without concomitant TMZ for 3-6 weeks, before beginning vaccination. All P30-EPS vaccines are given initially in a Priming Phase (on days 1, 4 (± 1 day), 8 (± 1 day), 15 (± 2 days), and 22 (± 2 days)), and then in a Booster Phase (on day 84 and day 140, both ± 7 days). During the Booster Phase on Day 84, patients will also be given 20 µg/kg Hiltonol® injections to administer at home every 2 weeks (± 2 days) until they return on Day 140. Patients will be contacted and/or sent a reminder prior to each injection at home to help ensure that these doses are not missed. Further details are available in Section 12.2.

Patients with evidence of radiographic progression according to Response Assessment in Neuro-Oncology (RANO) 2.0 criteria after radiation will be allowed to enroll on study as long as there is no evidence of new disease outside of the radiation field. Patients should continue to receive vaccines unless they experience unacceptable toxicity, decide not to continue receiving vaccines, or have disease progression.

For patients who require treatment with corticosteroids > 4 mg per day of dexamethasone (or equivalent) for mitigation of inflammatory response while they are on study, it will be recommended that patients initiate bevacizumab (7.5 mg/kg IV every 3 weeks) instead of increasing the steroid dose, if possible, as steroids may

interfere with the desired immune response to the investigational vaccine. It is strongly recommended that patients should not be receiving bevacizumab prior to vaccine 1. If patients are started on the radiation necrosis dose of bevacizumab for the purpose of managing intracranial inflammatory responses, the vaccine/return to clinic schedule for this study will not change. The bevacizumab schedule will be independent of the vaccine schedule, since it will be provided clinically, and will be managed by the oncology office administering this medication.

Baseline bloodwork for subclinical manifestations of autoimmunity as outlined in Section 12.6.5 will be taken on all subjects prior to vaccine #1 and then only repeated if clinically indicated. Bloodwork for immunological monitoring will be taken at baseline, at vaccinations 1, 5, 6, and 7 before the vaccine is given (days 1, 22, 84, and 140). The total amount of blood required for this purpose will be about 90 mL. Peripheral blood for immunologic immune monitoring will be delivered to the dedicated lab for processing. Further details are available in the ETAPA correlative laboratory manual.

Magnetic resonance (MR) images will be obtained after completing XRT/TMZ for baseline measurements and to assess progression. Patients will then be imaged at visits prior to receiving vaccines #5, #6, and #7. The RANO 2.0 criteria will be used for assessment of response and pseudoprogression following treatment [62].

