9.1.3 Dose Modification

In the event of DLT at the initial dose level of 300 µg/peptide/dose (see Section 15.5.1 for rules for dose escalation), the dose of the P30-EPS vaccine dose will be de-escalated to 200 µg/peptide/dose. See Section 15.5.1.2 for possible actions if 200 µg/peptide/dose is deemed unsafe. No dose modifications are allowed within an individual patient.

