9.1.4 Safety Considerations

Management of Toxicities

If a Grade 3 NCI CTCAE (Version 5) or greater toxicity is seen that is not attributable to a concomitant medication, co-morbid event, or radiographically or clinically documented disease progression, the next study treatment for that patient will be withheld for up to 2 months or until the toxicity improves to a Grade 2 or less. However, planned procedures requiring hospitalization or long-term clinical decline that are clearly not related to the study vaccine will not be considered an unacceptable toxicity nor will such patients have immunizations withheld.

In an abundance of caution, the current study has implemented an extended post-vaccine monitoring period in which the patients are observed in clinic with regular vital signs monitoring.

Patients will receive their 1st vaccine in the Oncology Treatment Center (OTC) and will receive a normal saline bolus by intravenously (IV) prior to vaccine administration. The IV saline lock used for the bolus will remain in place for all patients during the post-vaccine monitoring period for the purpose of quick administration of additional fluids and/or medication should either be necessary. Supportive medications for post-vaccine reactions may include the following per institutional guidelines:

- Sodium chloride NS bolus 20 mL/kg
- Benadryl 1 mg/kg IV push

- Solu-medrol 2 mg/kg IV push

Patients on study who experience a significant post-vaccine reaction at any point (i.e., \geq Grade 2 toxicity thought to be possibly, probably, or definitely related to study vaccine), but who are not removed from study, will receive a normal saline bolus by IV prior to vaccine administration for all subsequent vaccines and the IV saline lock will remain in place as a precautionary measure, in case supportive medications are needed. Patients on study who have never experienced a post-vaccine reaction or only experienced a Grade 1 toxicity with earlier vaccines will not be required to have an IV saline lock placed prior to administration of subsequent vaccines. The treating provider may opt to proceed with the IV saline lock though if a patient experienced a mild post-vaccine reaction with previous vaccines.

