3	Fever $\geq 38^{\circ}\text{C}$ with hypotension requiring 1 vasopressor with or without vasopressin and/or hypoxia requiring high-flow nasal cannula (>6 L/minute), facemask, nonrebreather mask, or venturi mask not attributable to another cause	If grade 3 toxicity develops where fluid resuscitation and 1 low dose vasopressor are not sufficient to reverse the hypotension, the patient will be transferred and monitored closely in the emergency department. All patients with grade 3 toxicity will receive immunosuppressive agents including corticosteroids, such as 2mg/kg Solu-medrol. In severe cases, Tocilizumab, antihuman IL-6R mAb, will be administered. This drug is stocked in the Duke pharmacy.
4	Fever $\geq 38^{\circ}\text{C}$ with hypotension requiring multiple vasopressors (excluding vasopressin) and/or hypoxia requiring positive pressure (e.g., CPAP, bilevel positive airway pressure, intubation, mechanical ventilation) not attributable to another cause	All patients with immediate, life-threatening toxicity will be treated with full support, including mechanical ventilation, immunosuppressive agents, Tocilizumab to prevent inflammatory cascade, and close comprehensive organ monitoring.

Note: The associated constitutional symptoms may be reported, but do not affect CRS grade per ASTCT Consensus Grading Guidelines.

Please refer to Section [13.1](#) for details on AE assessments and reporting.

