10.1.4 Dispensing and Preparation

Patients will receive the P30-EPS vaccines from ICS directly to the clinic or OTC under the supervision of the research nurse, or designee. The patient's name, Study ID, DoB, and Duke history number will be double-verified prior to vaccine administration, as is standard Duke procedure. The P30-EPS peptide and Hiltonol®

solution will be mixed in the ICS (see Section 10.1.2), transported to the clinic, and vaccinations will be given intramuscularly in the thigh. With each injection, the side of the body will be alternated in order to maximize systemic effect and minimize potential for site reactions.

Following administration of a P30-EPS vaccine, the first 6 patients (first 3 CMV seropositive and the first 3 CMV seronegative) on study will be retained for observation. These patients will be retained for 4 hours after the first 3 vaccines administered during the Priming Phase for observation, including regular vital signs monitoring every 30 minutes for a total of 8 sets of vital signs. If a patient experiences no vaccine injection reactions following the first three vaccines (Refer to Section 9.1.4 for background information on injection reactions experienced in a related adult study), the observation time following the subsequent vaccine injections may be decreased to two hours with a total of 4 sets of vital signs and eventually to 30 minutes with one set of vital signs at the discretion of the treating sub-investigator. If a patient experiences a post-vaccine Grade 3 or higher unacceptable reaction at any point, the monitoring period will revert to 4 hours until such time as he/she has 2 consecutive vaccines with no reaction. It will not be considered a deviation if the vitals are not captured exactly at the 30-minute time mark. As long as the patient is monitored for the protocol-specified amount of time, and as long as the correct number of sets of vitals have been collected for that time period, the patient will be considered sufficiently monitored. The PI or sub-investigator may extend monitoring periods at any given visit if they feel it is clinically indicated for the patient's safety.

If the first 6 patients do not experience Grade 3 or higher unacceptable toxicity, the 4 hours monitoring will only be required after the first vaccine for subsequent patients. After the first 6 patients have been enrolled, the study team will review the data and decide if 4-hour monitoring should be continued.

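### The Section 9.1.4 hold overlaps with the Section 9.1 stop for unacceptable toxicity and, as worded, allows same-dose vaccination after a related Grade 4 event or at 2 months with Grade 3 toxicity still present

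*Combined protocol and SAP*

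**What the plan says.** Section 9.1 (Study Design) gives the continuation rule: "Patients should continue to receive vaccines unless they experience unacceptable toxicity, decide not to continue receiving vaccines, or have disease progression". Of the three exceptions, refusal and progression end treatment, and nothing marks the toxicity exception as only a pause.

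Section 9.1.4 (Safety Considerations) covers toxicity of Grade 3 or greater that is not put down to a concomitant medication, a co-morbid event or documented progression. The next study treatment "will be withheld for up to 2 months or until the toxicity improves to a Grade 2 or less". The following sentence says that planned hospital procedures and long-term decline clearly unrelated to the vaccine "will not be considered an unacceptable toxicity nor will such patients have immunizations withheld". For Grade 4 cytokine release syndrome (CRS), Table 1 gives acute care only: "All patients with immediate, life-threatening toxicity will be treated with full support".

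Section 9.1.3 adds: "No dose modifications are allowed within an individual patient".

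Section 10.1.4, in its paragraph on observing the first 6 patients, says: "If a patient experiences a post-vaccine Grade 3 or higher unacceptable reaction at any point, the monitoring period will revert to 4 hours", and this lasts "until such time as he/she has 2 consecutive vaccines with no reaction".

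Three other sections touch on stopping. Section 9.1.6 mentions unacceptable toxicities that require discontinuation without saying which they are. Section 12.5.1 lists adverse events, with no grade, among possible reasons for withdrawal by the investigator. Section 12.3 ends treatment at progression or completion and does not name toxicity.

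**The concern.** A clinician who follows 9.1 stops vaccination after an unacceptable toxicity. A clinician who follows 9.1.4 pauses it, and 9.1.3 then fixes the resumed dose at the one that preceded the event. For most recovered Grade 3 events this is an ordinary choice between stopping and rechallenge, which the protocol should state.

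Two cases carry more risk. The hold has no Grade 4 limit. It also has two end conditions joined by *or*, so on its literal wording it can lapse at 2 months with Grade 3 toxicity still present. What is at stake is participant safety and consistent handling of the same event, not the validity of the primary analysis.

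**Working it through.** The point is textual, so the rules are compared first. The arithmetic only sizes it.

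**Do the two rules cover the same events?**
- Under 9.1.2.1, an unacceptable toxicity is a Grade 3 or higher event, at least possibly attributable to the regimen, within 30 days of a vaccine, subject to listed exemptions.
- The 9.1.4 trigger is any Grade 3 or higher toxicity not assigned to one of three other causes.
- An unacceptable toxicity with no such other cause therefore meets both rules: 9.1 lists it as a reason not to continue, and 9.1.4 as a reason to hold.
- The hold is also wider. It catches Grade 3 events that 9.1.2.1 does not call unacceptable, such as fever under 72 hours. For those there is no conflict with 9.1, so the overlap is partial.

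**What does the hold leave open?**
- Grade 4: the trigger includes it, improvement to Grade 2 ends the hold, and neither Table 1 nor Sections 9.1.6, 12.3 or 12.5.1 bar another dose.
- Grade 3 persisting at 2 months: no action is given, and reaching the time limit is itself one of the two ways the hold ends.

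**How much delay does the 2-month limit give?** Two calendar months are 59 to 62 days. For the related pp65 peptide trial, Section 7.2.2 reports: "The reactions typically occurred 2-4 hours after vaccine administration". Same-day onset is therefore the relevant case. At nominal days:
- Event at #5 (Day 22): 22 + 59 = 81 to 22 + 62 = 84. Vaccine #6 is due on Day 84 (window 77 to 91), so the limit does not delay it.
- Event at #6 (Day 84): 84 + 59 = 143 to 84 + 62 = 146. The window for #7 is 140 ± 7, or Day 133 to 147, so the limit expires inside it.

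**Exposure if a patient resumes.** Vaccines left after an event at #k are 7 − k: 6 for k = 1, 2 for k = 5, 1 for k = 6, 0 for k = 7. Each carries 3 × 200 µg = 0.6 mg to 3 × 400 µg = 1.2 mg of peptide. Events up to #6 also leave three home Hiltonol injections (Section 10.2.1). Section 9.1.4 does not say whether the hold covers them.

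**How many patients?** The documents give no rate for Grade 4 or unresolved Grade 3 related events. At an assumed 1% to 5% of the maximum 36 patients: 36 × 0.01 = 0.36 and 36 × 0.05 = 1.8.

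**Day 140 data lost if such patients stop.** Section 15.9 plans 24 patients at the MTD with 75% giving Day 140 data: 24 × 0.75 = 18.
- Grade 4 and 2-month stops, at the same assumed rates: 24 × 0.01 × 0.75 = 0.18 to 24 × 0.05 × 0.75 = 0.9.
- If the sponsor also stops after every other Grade 3 unacceptable toxicity, at an assumed 5% to 1 in 6: 24 × 0.05 × 0.75 = 0.9 to 24 × (1/6) × 0.75 = 3.0.

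At the assumed rates these are upper bounds, because Day 140 blood is drawn before #7 and a stop after #7 loses none.

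**The case against.** The best defence is that the two sections can be read together: hold the Grade 3 events that 9.1.2.1 exempts, and stop for unacceptable toxicity under 9.1. Section 9.1.6 leans that way. This shows that the conflict is partial, and a reader who infers a flat contradiction goes too far. But 9.1.4 does not limit its hold to exempt events, so the harmonised reading has to be supplied by the reader.

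Second, removal is contemplated. Section 9.1.4 itself refers to patients with related reactions who stay on study, 12.5.1 allows withdrawal for adverse events, 9.4 requires the reason for stopping to be documented, and 13.1.1 provides weekly review at what is a single centre. These safeguards stand and lower the risk. None gives a grade, a time limit or an order of precedence.

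Third, the 2-month limit may be meant as a maximum hold followed by discontinuation. Section 7.2.2 also reports that most patients with reactions in the related trial went home the same or next day, a few after 2 to 4 days, and that the most significant reactions listed were no higher than Grade 3. Toxicity unresolved at 2 months is therefore probably rare. Even so, the maximum-hold meaning is not written.

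Fourth, a reader might take the 10.1.4 clause as proof that re-dosing after unacceptable reactions is current policy. It sits in the paragraph on the first 6 patients, who had been treated by 4/24/2024, so it is weak support. It needs aligning but does not carry the point.

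Finally, vaccination after manageable reactions looks deliberate: Section 12.2.2 allows prednisone premedication at later visits. That is a reason to leave rechallenge after recovered Grade 3 events to the sponsor.

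**Conclusion.** The point holds in a limited form. Sections 9.1 and 9.1.4 overlap for unacceptable toxicities without precedence. The hold as worded permits same-dose vaccination after a related Grade 4 event, or at 2 months with Grade 3 toxicity still present. This is worth correcting for participant safety.

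The number affected is probably small: 0.4 to 1.8 of 36 patients, resting wholly on the assumed 1% to 5%. The timing results assume nominal visit days and same-day onset.

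Three stronger inferences are not supported:
- That the sponsor intends to vaccinate through unresolved toxicity. The wording is loose, but no text states that intent.
- That the safety results are compromised. A patient with a DLT or unacceptable toxicity is counted whether or not vaccination continues, so the DLT endpoint and the Table 4 thresholds are unaffected.
- That patients with an unacceptable toxicity at a dose later found to exceed the MTD must be stopped. That would be a new design rule, not the repair of a defect in the text.

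**What to change.** Keep the 9.1 sentence and add a cross-reference: *see 9.1.4 for toxicities that are held rather than stopped*.

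In 9.1.4, replace the hold wording with: *the next study treatment, including home Hiltonol, will be withheld until the toxicity improves to Grade 2 or less. P30-EPS and home Hiltonol are permanently discontinued after (a) any Grade 4 unacceptable toxicity as defined in 9.1.2.1, or (b) any unacceptable toxicity as defined in 9.1.2.1 that has not improved to Grade 2 or less within 2 months.* The text should also say that the 2 months run from onset.

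For other Grade 3 unacceptable toxicities, the sponsor should state in 9.1.4 either that the 9.1 stop applies or that same-dose rechallenge is allowed after recovery, and align the 4-hour monitoring clause in 10.1.4.

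Tying (a) and (b) to 9.1.2.1 keeps its exemptions. An exempt Grade 3 event lasting beyond 2 months would wait for recovery but would not force a permanent stop.

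The cost is amendment wording in three sections, with no added visits or tests. A few patients may stop early and give no Day 84 or Day 140 sample: for (a) and (b), at most about 0.2 to 0.9 of the 18 at the assumed rates. Choosing the stop for other Grade 3 unacceptable toxicities would cost a further 0.9 to 3.0 at most under its own assumed rates, though 9.1 already points to that stop.
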